Multidisciplinary behavioral therapy reduces rumination

NCT05232097

Study protocol with statistical analysis plan 2024-9-10

Study protocol with statistical analysis plan

Background

Rumination is a disorder of the gut-brain interaction characterized by repetitive regurgitation of ingested food that is followed by remastication and swallowing or spitting but without preceding retching or nausea (1, 2). The Rome IV rumination criteria include symptom onset six months prior to diagnosis and persistent symptoms for the last three months (3). Rumination is caused by subconscious but volitional contractions of the abdominal muscles resulting in intragastric pressure peaks of ≥ 30 mmHg that can be detected by performing esophageal high-resolution manometry using a solid test meal (4).

Biofeedback can reduce rumination by teaching the patients to control abdomino-thoracic muscle activity by following electromyography during eating. This has been proven in both open and randomized, placebo-controlled studies (5-6). Behavioral therapy consisting of diaphragmatic breathing exercises has been shown to reduce rumination in an open setting (7). We have used habit-reversal therapy with diaphragmatic breathing exercises successfully at our center to treat patients with supragastric belching (8). Our case report shows that rumination could be reduced by combining diaphragmatic breathing with abdomino-thoracic muscle relaxing exercises performed by a physiotherapist (9).

Data from randomized studies show that multidisciplinary therapy performed by a group comprising gastroenterologists, dietitians, hypnotherapists, psychiatrists and biofeedback physiotherapists is superior to standard gastroenterologist therapy in improving symptoms, psychological state, quality of life and costs in functional gastrointestinal disorders. The difference maintains up to 12 months of follow-up (10, 11).

We wanted to test the efficacy of a multidisciplinary, behavioral approach in treating patients with rumination in the present study. This study was approved by the Ethics Committee of Helsinki University Hospital (HUS/2118/2021) and by the Helsinki University Hospital Abdominal Center (HUS/23/2022). The study was registered at Clinical Trials as study number NCT05232097.

Objective

The primary objective was a reduction of ≥ 2 of the rumination score measured by question 32 of the Rome IV diagnostic questionnaire for adult functional disorders (Rome IV) at baseline and at the 6-month control. Secondary objectives were improvement of HRQoL and functional capacity scores, reduction of anxiety and depression scores, and disappearance of intragastric pressure peaks in esophageal manometry at the 6-month control.

Patients

We recruited rumination patients from gastroenterology outpatient clinics to our study at the Helsinki University Hospital during the study period of Jan. 1, 2022, to Dec. 31, 2023.

The inclusion criteria for the study included age between 15-70 years, Finnish as the native language, fulfillment of the clinical Rome IV rumination criteria, a rumination score of ≥ 6 in the Rome IV diagnostic questionnaire for adult functional disorders (rumination occurring most days a week),

previous gastroscopy, esophageal manometry and MII-pH. We aimed to recruit patients, who had previously had esophageal manometry performed with intragastric pressure increases ≥ 30 mmHg immediately preceding the rumination experienced by the patient, suggestive of rumination. Patients with only a clinical diagnosis of rumination syndrome were also accepted in the study, because previous to our study, Nutridrink instead of a solid meal was used when performing standard esophageal manometry in our institution and thus might not always detect rumination.

The exclusion criteria comprised large hiatal hernia, severe esophagitis, previous fundoplication, eating disorder, BMI under 14, pregnancy, significant cognitive disorder, and any other condition hindering outpatient visits.

Study protocol

At the baseline visit, cases were checked to ascertain whether they fulfilled the inclusion or exclusion criteria. Previous conditions, investigations, use of medications, and symptoms were registered. All patients obtained written information about the study, about the behavioral and functional nature of rumination, and its therapy including diaphragmatic breathing exercises and thoracic and abdominal muscle relaxations. Written consent was obtained from all patients.

From the baseline visit the patients were referred to the speech therapist for five one-hour sessions, and to the physiotherapist for two one-hour sessions and to the psychologist's and the dietitian's consultation.

Symptoms, HRQoL, depression, anxiety, and functional capacity were evaluated by questionnaires given to the patients and weight were defined at onset of the study and at the 6-month control. Esophageal manometry with a pancake meal (191 kcal) was performed at the 6-month control. The study protocol is displayed in the figure below (Figure 1).

Questionnaires

Symptom severity was evaluated by the Rome IV questionnaire for adult functional disorders (12). The question 32 of the Rome IV diagnostic questionnaire for adult functional disorders scores the rumination frequency as follows: "In the last 3 months, how often did food come back up into your mouth after you swallowed it ?, 0 = never, 1= fewer than 1 day a month, 2 = 1 day a month, 3 = 2-3 days a month, 4 = 1 day a week, 5 = 2-3 days a week, 6 = most days, 7 = every day, 8 = multiple times per day or all the time".

Depression was evaluated by the Beck Depression Inventory (BDI), anxiety by the Beck Anxiety Inventory (BAI), HRQoL by the 15D, a 15-dimensional measure of health-related quality of life and functional capacity by the World Health Organization disability assessment schedule 2.0 (WHODAS 2.0) (13-16). The patients filled out the questionnaires at home and mailed them to the hospital.

Behavioral therapy

The therapy comprised psychoeducation about the nature of rumination as a behavioral disorder and means of dealing with the symptom including diaphragmatic breathing exercises and guided eating performed by the speech therapist, and mind-body oriented physiotherapy, all aiming at habit reversal.

The patients were first taught the mechanisms of rumination at the speech-therapist visits. We considered it essential for the study's success for the patients to understand the functional nature of rumination. The next step was to teach them diaphragmatic breathing and to relax abdominal muscles. Finally, the patients were trained to apply these exercises during meals and to continue them at home.

The mind-body oriented physiotherapist approached the patients to improve body awareness – which consists not only of sensing position and movement of the body in space – but also of sensing the internal state of the organs – and to understand that signals from the stomach entering conscious awareness are modified by mental processing. The physiotherapist also encouraged the patients to freely express their concerns and worries during sessions to enhance abdominal and thoracic muscle relaxations. The physiotherapy consisted first of manual therapy of the tensed regions of the neck, chest and abdomen, and of relaxation exercises, and imagery training to find one's inner refuge, all aiming to reduce overexcitement and achieve body and mind relaxation. Second, breathing exercises to relax the thoracic and abdominal muscles were performed at the therapy sessions. Third, the patient was guided to practice imagery training, relaxation exercises, and breathing exercises at home.

Psychologist and dietitian consultations

The patients were referred to a psychologist for assessment of psychiatric symptoms. The psychologist's consultation included psychoeducation about how stress and anxiety affect rumination symptoms, and how to improve the stress and anxiety management to enhance rehabilitation of the rumination syndrome. We considered it reasonable to consult a psychologist trained in functional behavioral disorders first rather than sending all patients directly to the psychiatrists. A referral to a psychiatrist was recommended in the case of more severe psychiatric conditions.

[figure not shown]
The patients were referred to a dietitian trained in functional behavioral disorders for psychoeducation, to evaluate food and meal and related mental threats, and to ensure a sufficient diet. The primary goal of the dietitian's psychoeducation was to ensure that patients did not have negative expectations regarding food or nutrients. It is common in functional diseases that patients develop learned experiences and expectations that become self-predictive. The dietitian interviewed the patients to discover which food products the patients avoided due to them provoking rumination or other gastrointestinal symptoms such as diarrhea, to learn if rumination played a role in managing anxiety, and to discern if the patients had lost weight prior to or during the study. No special diet instructions or foods were recommended to be avoided due to rumination. The dietary goal was to normalize eating.

Statistical analysis

SPSS software was used to perform the statistical analysis. The question 32 of the Rome IV diagnostic questionnaire for adult functional disorders was used for the sample size calculation. The hypothesis was that the mean (\pm standard deviation) self-perceived frequency of rumination at baseline would be 6 ± 2 (most days a week) because this was the inclusion criteria for the study and the symptom improvement after therapy would be ≥ 2 resulting in the score of 4 ± 2 (once a week) at the 6-month control. Using the Sample Size Calculator of ClinCalc.com the number of patients required was 8 to obtain 80% power and significance of $P < 0.05$. The non-parametric Wilcoxon's signed rank test and Mann-Whitney test for the analysis of related samples were used for the

comparison of differences in the distributions of variables between the baseline and the 6-month control except for the 15 dimensions of HRQoL which were analyzed by the paired samples t-test. The independent samples t-test was used to compare the mean 15D results of the patients at baseline with those of age-standardized general Finnish population. Apart from the manometry and 15D results which are displayed as means and standard deviations, all other results are displayed as medians and interquartile ranges.

Figure 1.

References

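### The primary objective is a drop of at least 2 points on question 32, but the analysis tests only for any change and names no summary, interval or success rule to set against 2

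*Combined protocol and SAP*

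**What the plan says.** The Objective section puts the threshold into the primary objective itself: "The primary objective was a reduction of ≥ 2 of the rumination score measured by question 32" of the Rome IV questionnaire, between baseline and 6 months. It does not say whether this is a target for the group or for each patient.

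In the Statistical analysis section the 2 points return only in the sample-size hypothesis, where "the symptom improvement after therapy would be ≥ 2 resulting in the score of 4 ± 2" is assumed from a baseline of 6 ± 2. From this, "the number of patients required was 8 to obtain 80% power" at P < 0.05. The Wilcoxon signed-rank and Mann-Whitney tests are then assigned to the "comparison of differences in the distributions of variables between the baseline and the 6-month control". For display, means and standard deviations are reserved for manometry and 15D, and "all other results are displayed as medians and interquartile ranges".

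Entry requires "a rumination score of ≥ 6 in the Rome IV diagnostic questionnaire for adult functional disorders", and the top of the scale is "6 = most days, 7 = every day, 8 = multiple times per day or all the time", so every baseline score is 6, 7 or 8.

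**The concern.** An objective with a number in it needs an analysis that can be held against that number. The plan has no estimate of change designated for comparison with 2, no confidence interval for the change, no count of patients who fall by at least 2, no test against a 2-point shift and no rule for declaring success.

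The practical risk lies in the reporting. A significant signed-rank result on question 32 could be presented as achieving the primary objective when it shows only that scores changed. Readers would then credit the therapy with a 2-point improvement that the analysis had not examined.

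**Working it through.** **Inputs.** Threshold 2 points (Objective). Scores 6 ± 2 to 4 ± 2, 80% power, P < 0.05, N = 8 (Statistical analysis). Baselines 6 to 8 (Patients, Questionnaires). The number of patients actually analysed is not in the document, so the patterns below use the required 8. They assume no standard deviation.

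**The plan's own figure.** N = 8 follows from a one-sample normal approximation with SD 2, difference 2, two-sided 5% and a null of zero change:

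n = [SD × (z₀.₉₇₅ + z₀.₈₀) / difference]² = [2 × (1.960 + 0.842) / 2]² = 7.85, rounded up to 8.

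The stated power therefore matches a test for any change, not a test that the drop is at least 2.

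**Does P < 0.05 show the objective was met?** Exact two-sided signed-rank P by full enumeration of signs, zeros dropped, mid-ranks for ties:

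| Pattern, n = 8 | Exact P | Mean drop | Median drop | Drop ≥ 2 |
|---|---|---|---|---|
| A: all fall by 1 | 2/256 = 0.0078 | 1.0 | 1 | 0/8 |
| B: six fall by 1, two unchanged | 2/64 = 0.031 | 0.75 | 1 | 0/8 |
| C: six fall by 2, two unchanged | 2/64 = 0.031 | 1.5 | 2 | 6/8 |

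A and B are significant although no patient reaches 2. B and C have the same P, yet 0 of 8 patients reach 2 in one and 6 of 8 in the other. In C a group target is missed on the mean (1.5) and met on the median (2).

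**Does the display show it?** Suppose the medians are given per visit. Take baseline scores 6, 6, 6, 6, 8, 8, 8, 8 and the eight 6-month scores 4, 5, 5, 5, 5, 7, 7, 7. The display reads 7 (6–8) at baseline and 5 (5–7) at 6 months, a fall of 2, however the scores are paired:

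| Pattern | 6-month scores in baseline order | Drops | Median drop | Drop ≥ 2 | Signed-rank P |
|---|---|---|---|---|---|
| D | 5, 5, 5, 5, 4, 7, 7, 7 | 1, 1, 1, 1, 4, 1, 1, 1 | 1 | 1/8 | 2/256 = 0.0078 |
| E | 7, 7, 7, 4, 5, 5, 5, 5 | −1, −1, −1, 2, 3, 3, 3, 3 | 2.5 | 5/8 | 24/256 = 0.094 |

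Over all pairings of these 16 scores, the number with a drop of at least 2 runs from 1 to 5 and the median paired change from 1 to 2.5. The mean drop is 11/8 = 1.375 in every pairing, because a difference of visit means equals the mean paired change.

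**Precision of a responder count at n = 8.** Clopper-Pearson 95% intervals: 0/8 gives 0–37%, 1/8 gives 0.3–53%, 5/8 gives 24–91%, 6/8 gives 35–97%. For a median change, the smallest to the largest of the eight changes covers 1 − 2/256 = 99.2%. The next narrower pair, second to seventh, covers 1 − 18/256 = 93.0%, below 95%.

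**The case against.** Sizing on an expected effect and testing against no change is ordinary practice, and the plan nowhere claims that P < 0.05 would establish a drop of 2. That stands as a description of the sizing. It does not close the gap, because here the 2 points are the stated primary objective and not only a planning assumption.

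The 6 ± 2 to 4 ± 2 wording suggests a target for the group. On that reading, summaries of the two visits do bear on the objective, at least descriptively. This also stands. A reader might infer that none of the planned output answers the primary question; the document does not support so strong a statement. What is missing on the group reading is the named summary, its interval and the success rule.

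A reader might also take it as settled that the display will be two visit medians. That is the likely meaning but an inference: the text does not say per visit, and a median of the change is not excluded. It would still come without a confidence interval or a rule.

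Finally, patterns D and E are constructed. They show what is possible, not what is likely, and they matter only on a per-patient or paired-change reading. On a group-mean reading they are identical (1.375). The Mann-Whitney test, which ignores pairing and is also named in the plan, gives both the same P of about 0.036 (asymptotic). It would be wrong to infer from them that the plan's P value generally runs against the responder count. Patterns A and C carry the point without them.

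**Conclusion.** The concern holds in this form: the plan sets a threshold as its primary objective and specifies no way to judge it. A significant result is compatible with 0 of 8 patients reaching 2 (P = 0.0078), and the verdict on a group target can turn on whether mean or median is used (1.5 against 2 in pattern C). On a group reading the planned display addresses the target descriptively and without an interval. On a per-patient or paired-change reading nothing planned addresses it, since one pair of visit summaries can fit anything from 1/8 to 5/8 patients with a drop of at least 2.

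The worked patterns rest on n = 8 and on exact signed-rank calculations; the display comparison also assumes medians per visit. The finding that no summary, interval or rule is named rests on the text alone. This should be fixed. It does not show that the therapy missed its target, or that the sample size must be redone.

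**What to change.** 1. State in the objective whether the 2-point reduction is a target for the group or for each patient.
2. If group, name the summary compared with 2 (mean paired change, median paired change, or difference between visit summaries) and report it with a 95% confidence interval. If per patient, say whether a target proportion applies or the proportion is only estimated.
3. In either case, report the number and proportion of patients with a drop of at least 2, with an exact 95% interval, the denominator and the number lacking a 6-month score.
4. Treat the signed-rank P as evidence of any change only, and do not offer it by itself as meeting the objective.
5. Label the added analysis with the date it was specified. The title line reads "Study protocol with statistical analysis plan 2024-9-10", after the study period that the Patients section ends on Dec. 31, 2023.

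The cost is a few sentences and one table from the question 32 scores the study collects anyway, with no new data and no re-sizing. The downsides are real: the intervals will be wide at this size, a claim of at least 2 points becomes harder to make, and the analysis may have to be called post hoc.

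### Disappearance of pressure peaks is a yes/no outcome that only patients with earlier peaks can show, but the plan displays manometry as means and SDs and plans no count of patients who became peak-free

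*Combined protocol and SAP*

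**What the plan says.** All references are to the combined protocol and SAP.

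- **Objective:** the secondary objectives end with "disappearance of intragastric pressure peaks in esophageal manometry at the 6-month control". The other stated objectives, primary and secondary, are all questionnaire scores.
- **Background:** rumination is described through "intragastric pressure peaks of ≥ 30 mmHg that can be detected by performing esophageal high-resolution manometry using a solid test meal".
- **Patients:** the investigators aimed to recruit people whose earlier manometry had shown "intragastric pressure increases ≥ 30 mmHg immediately preceding the rumination experienced by the patient, suggestive of rumination". This was an aim and not a condition of entry: "Patients with only a clinical diagnosis of rumination syndrome were also accepted in the study". The reason given is that, before the study, "Nutridrink instead of a solid meal was used when performing standard esophageal manometry in our institution and thus might not always detect rumination". The inclusion criteria do list "previous gastroscopy, esophageal manometry and MII-pH", so every patient should have had some manometry before entry.
- **Study protocol:** "Esophageal manometry with a pancake meal (191 kcal) was performed at the 6-month control".
- **Statistical analysis:** manometry and 15D results are displayed as means with SDs, and everything else as medians with interquartile ranges. Wilcoxon and Mann-Whitney tests are named for baseline to 6-month comparisons, apart from the 15 dimensions of the 15D. No count, proportion or paired yes/no analysis is named, and no population is stated for manometry.

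**The concern.** The objective asks a question of each patient: were there peaks before therapy, and are they gone at 6 months? The planned display is an average. An average of pressures, or of numbers of peaks, does not say in how many patients the peaks went away. The plan does not say which patients enter that average either. If it includes people with no documented peaks at entry, it mixes patients who could show the outcome with patients who may have had nothing to lose.

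What is at stake is the only objective not based on a questionnaire, in a study where every enrolled patient is referred for therapy and no control group is described. Readers will look to it for objective support of the symptom scores. Under the plan as written, they would get a number that does not say whether the objective was met.

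**Working it through.** **1. The plan's own figure.** The Statistical analysis section gives 8 patients for question 32, from a change of 2, an SD of 2, 80% power and P < 0.05. Assuming a two-sided test and a one-sample normal approximation, n = ((1.960 + 0.842) × 2 / 2)² = 7.85, rounded up to 8. The figure reproduces. It concerns the question 32 score only; no size is stated for manometry.

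**2. Can a mean answer the objective?** The documents give no pressures, so these are assumed. Take six patients with pre-therapy peaks and 6-month maxima of 10, 10, 10, 45, 45 and 45 mmHg.

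- Mean = (3 × 10 + 3 × 45) / 6 = 165 / 6 = 27.5 mmHg.
- Each value lies 17.5 from the mean, so SD = √(6 × 17.5² / 5) = √367.5 = 19.2 mmHg.
- Patients with a maximum of at least 30 mmHg: 3 of 6.

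The mean is below the threshold while half the patients still have peaks. The result does not hang on these exact values. If half the patients have maximum a and half have maximum b (b at least 30), the mean is (a + b) / 2, which is below 30 whenever a is below 60 − b. For b = 45, any a below 15 will do; for b = 30, any a below 30.

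**3. What the matching summary would look like.** The number of patients with documented entry peaks is not given, so n is assumed.

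- 3 peak-free of 6: 50%, exact (Clopper-Pearson) 95% CI 11.8% to 88.2%.
- Best case, all n peak-free: the lower limit is 0.025^(1/n), as below.

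| n with entry peaks | Lower 95% limit if all become peak-free |
|---|---|
| 2 | 16% |
| 4 | 40% |
| 6 | 54% |
| 8 | 63% |

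**4. Why the denominator should be written down.** Assume 8 patients, 6 with entry peaks, 3 of whom become peak-free. Among those who could show the outcome the result is 3/6 = 50%. Counted over all 8, the peak-free share is 3/8 (38%) if both other patients show peaks at 6 months and (3 + 2)/8 = 5/8 (63%) if neither does. No section plans such an all-patient rate; the example shows only that the same data give different figures when the denominator is left open.

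**The case against.** The best defence has four parts.

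- **The word itself.** Disappearance presupposes earlier presence, so the restriction to patients with entry peaks may have been intended. This is fair, and the wording does lean that way. It settles who could count, but not how the outcome is counted, and the stated display still contains no count.
- **Means do not forbid counts.** This is true. But a plan should name the summary by which its own objective is judged, and the one it names does not do that.
- **The threshold is in the document.** This is also true. The 30 mmHg figure appears in Background and Patients, so the gap is only that it is not tied to the 6-month outcome. A reader might infer that these two sections give rival scoring rules, because only Patients mentions a link to felt rumination. The text does not support that: Background describes the mechanism of rumination and sets no rule. Making the link part of the main definition would also change the objective. A patient with persisting peaks who felt no rumination during one test meal would count as a success, which can favour the therapy in an open study.
- **Low weight.** The outcome is secondary, every count and pressure above is assumed, and the result will be imprecise whatever is done. This limits the importance of the point but does not remove it.

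A reader might also infer that tests before and after therapy used different meals and so cannot be compared. The Study protocol text says questionnaires were given and "weight were defined at onset of the study and at the 6-month control", and places the pancake-meal manometry only at 6 months. But Figure 1 is not shown and individual entry meals are not stated. A mismatch is possible but not documented. In patients with entry peaks, a change to a more sensitive solid meal would work against apparent success.

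**Conclusion.** The point holds. The objective is a yes/no change in patients with documented pre-therapy peaks, the study also accepted patients without them, and the planned means and SDs cannot show in how many patients the peaks disappeared. In the assumed example, a mean of 27.5 mmHg sits below the threshold while 3 of 6 patients still have peaks.

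Two stronger conclusions should be avoided. A reader might infer that the plan inflates success by counting patients without entry peaks as cleared. No section proposes this, and those patients could show peaks with a solid meal, since the earlier meal was said to be liable to miss rumination. A reader might also infer that the main result is weakened, but the question 32 endpoint and its sample size of 8 do not depend on manometry.

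The reading of the text is firm. The size is not, because the documents give no enrolment figure, no number of patients with entry peaks and no pressures. The change is worth making but does not decide the study.

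**What to change.** Add a few sentences to the Statistical analysis section:

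- **Main summary for this objective:** k/n, where n is the number of patients with documented pre-therapy peaks and a 6-month test, and k is the number of these who are peak-free at 6 months, with an exact 95% CI. Use the plan's own amplitude threshold of at least 30 mmHg at both times.
- **Sensitivity result only:** the same count, requiring the pressure rise to come directly before rumination that the patient feels.
- **Accounting:** state how many patients with entry peaks had no 6-month test, and list separately the 6-month results of patients without documented entry peaks.
- **Supplement:** keep means and SDs, and note each patient's entry test meal.
- **Labels:** call the definition post hoc if it was set after the data were seen. This is likely: the plan is dated 10 September 2024 and recruitment ran to 31 December 2023, so 6-month visits were probably due by about mid-2024. Call the result descriptive, because patients are selected on a positive entry test, which can by itself favour apparent improvement.

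The cost is wording and a look through existing records. Earlier manometry was an inclusion criterion, so no new test is needed. The drawbacks are a smaller denominator and a wide interval (assumed 3/6: 12% to 88%). Old reports that do not record the link to felt rumination would be unclassifiable in the sensitivity result.

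### Patients are selected on a high score of the primary-outcome item; if that reading is also the baseline, part of the fall is regression to the mean, which a single-arm comparison cannot separate from therapy

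*Combined protocol and SAP*

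**What the plan says.** - **Entry (Patients).** Patients need "a rumination score of ≥ 6 in the Rome IV diagnostic questionnaire for adult functional disorders", which the plan explains as symptoms on most days of the week.
- **Primary outcome (Objective).** "The primary objective was a reduction of ≥ 2 of the rumination score measured by question 32", comparing baseline with the 6-month control.
- **Scale (Questionnaires).** Question 32 runs from 0 to 8 with 3-month recall. Its top categories are "6 = most days, 7 = every day, 8 = multiple times per day or all the time".
- **Planning value (Statistical analysis).** The mean frequency "at baseline would be 6 ± 2 (most days a week) because this was the inclusion criteria for the study", falling to 4 ± 2; 8 patients are required for 80% power.
- **Timing (Study protocol, Questionnaires).** "At the baseline visit, cases were checked to ascertain whether they fulfilled the inclusion or exclusion criteria". The outcomes came from "questionnaires given to the patients and weight were defined at onset of the study and at the 6-month control". "The patients filled out the questionnaires at home and mailed them to the hospital".
- **Comparison (Study protocol, Statistical analysis).** All patients are referred to therapy from the baseline visit. No comparator group is described. Change is tested within patients by the signed-rank test.

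**The concern.** The entry criterion does not number its item, but its explanation matches category 6 of question 32, and the sample-size paragraph takes the expected question 32 baseline from the entry criterion. The item that selects patients is therefore evidently the item that measures success.

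An observed score is a patient's usual level plus error. Choosing patients because one reading is high also chooses readings whose error happens to be upward, and that error does not carry over to the next reading. The capped scale adds to the asymmetry: a patient enrolled at 6-8 can rise by at most 2 points but fall by up to 8. If the qualifying reading is the baseline, the expected change leans toward benefit by an amount that more patients do not reduce. The Background gives testing efficacy as the purpose, so it matters how much of the fall is credited to therapy.

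**Working it through.** **1. The plan's own figure.** Inputs from Statistical analysis: fall 2, SD 2, 80% power, P < 0.05 (two-sided assumed). n = [SD × (z0.975 + z0.80) / fall]² = [2 × (1.960 + 0.842) / 2]² = 7.85, rounded up to 8. The stated number reproduces. It counts the whole fall of 2 as effect, with no allowance for selection.

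**2. Can 6 ± 2 set the size?** No. Scores that all passed 6 or more on a 0-8 item lie in 6-8. A mean of exactly 6 then forces an SD of 0, and the SD cannot exceed 1 (half the scores at 6 and half at 8). The documents give no score distribution before selection and no test-retest reliability, so all three inputs below are assumptions.

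**3. Model.** The observed score is a true score plus independent error, with mean μ and SD σ before selection, rounded and clipped to 0-8. Patients are selected if the first reading is 6 or more, and there is no therapy effect. Reliability ρ is the share of variance due to the true score. Ignoring the cap, the expected fall is

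(1 − ρ) × σ × φ(a) / [1 − Φ(a)], with a = (5.5 − μ) / σ.

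Example, μ = 6, σ = 2, ρ = 0.7: a = −0.25, φ(a) = 0.387, 1 − Φ(a) = 0.599, so the fall is 0.3 × 2 × 0.646 = 0.39. On the rounded, capped scale it is 0.41.

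**4. Expected fall in points, rounded and capped scale, no therapy effect:**

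| SD | Mean | ρ = 0.5 | ρ = 0.7 | ρ = 0.9 |
|---|---|---|---|---|
| 1 | 4 | 1.13 | 0.74 | 0.35 |
| 1 | 5 | 0.67 | 0.44 | 0.21 |
| 1 | 6 | 0.30 | 0.20 | 0.09 |
| 1 | 7 | 0.08 | 0.05 | 0.025 |
| 2 | 4 | 1.37 | 0.85 | 0.32 |
| 2 | 5 | 0.98 | 0.61 | 0.23 |
| 2 | 6 | 0.65 | 0.41 | 0.16 |
| 2 | 7 | 0.38 | 0.24 | 0.09 |
| 3 | 4 | 1.62 | 1.02 | 0.37 |
| 3 | 5 | 1.27 | 0.80 | 0.30 |
| 3 | 6 | 0.95 | 0.61 | 0.23 |
| 3 | 7 | 0.68 | 0.44 | 0.17 |

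The range is about 0.02 to 1.6 points, or roughly 1% (0.025 / 2) to 81% (1.62 / 2) of the 2-point target. No cell reaches 2.

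**5. Effect on the test.** For n = 8, SD 2, means 5-7 and reliability 0.6-0.9, the exact signed-rank test declares a false improvement in 0.1% to 11.4% of simulated trials, against a nominal 2.5% in that direction. With large-sample p-values the figure is about 2% to 21%; the plan does not say which is used. The rate may therefore lie below or well above nominal.

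**The case against.** The strongest objection is that the premise is unproven. Nothing says that the eligibility reading was the form analysed. Eligibility was checked at the baseline visit, whereas the questionnaires were filled in at home and mailed, so a separate reading may exist. Figure 1, which sets out the study protocol, is not visible in the text available for this review. The sample-size sentence justifies a planning value; it does not identify a form. A reader might infer that one reading certainly served both purposes. The documents make that likely, but they do not establish it, so the point is conditional.

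The second objection is that the upper figures fit this population poorly. Candidates were already diagnosed clinic patients, the Rome IV criteria require persistent symptoms, and the item covers three months. At mean 5 and SD 2 only about 40% of candidates would score 6 or more, and nothing suggests that most diagnosed patients were below the threshold. At mean 7 the fall is 0.025 to 0.68 points over all assumed SDs and reliabilities. This stands as a reason to expect the low end. It does not show that the bias is zero.

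Third, regression to the mean is only one part of what a single-arm design leaves uncontrolled. That also stands: natural course and expectation are separate, and nothing proposed here addresses them.

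**Conclusion.** The concern holds conditionally. If the qualifying reading is the analysis baseline, the expected primary change is biased toward benefit, and the planned comparison cannot separate that part from therapy. The size cannot be determined from the documents. It is about 0.02 to 1.6 points over pre-selection means 4-7, SDs 1-3 and reliabilities 0.5-0.9, all assumed.

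Two stronger readings are not supported. One is that selection alone could produce the planned fall: it stays below 2 points in every scenario, so the result needs a qualified conclusion, not rejection. The other is that a narrow range bounds the artefact. Fixing the SD at 2, the mean at 5-7 and the reliability at 0.6-0.9 gives about 0.1 to 0.8 points, but the documents justify none of those limits, so that is not the full range.

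**What to change.** **Data already collected.** If a pre-therapy question 32 reading exists that was not used for eligibility, use it as the analysis baseline and say so. If none exists, conclude that scores were lower after therapy without attributing the whole fall to it. Any range shown for regression to the mean should vary mean, SD and reliability together and be labelled as assumed. The cost is a more cautious conclusion; no new data are needed.

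**Extension or repeat.** Collect one separate mailed question 32 reading after eligibility is settled and before the first therapy session, and make it the analysis baseline. The cost is one more mailed item and a smaller expected fall, which the sample size should reflect.

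**Limit of the correction.** It is complete only if the errors of the two pre-therapy readings are independent. Overlapping 3-month recall windows make some correlation likely. At SD 2, means 5-7 and reliability 0.6-0.9, the artefact of 0.09-0.80 points falls to 0.04-0.37 at an assumed error correlation of 0.5, and to 0.02-0.19 at 0.25.
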